8.0 STUDY ASSESSMENTS AND PROCEDURES

- Study procedures and their timing are summarized in the SoA ([Table 1](#)).
- Protocol waivers or exemptions are not allowed.
- Immediate safety concerns should be discussed with the Medical Monitor immediately upon occurrence or awareness to determine if the patient should continue or discontinue study treatment.
- Adherence to the study design requirements, including those specified in the SoA, is essential and required for study conduct.
- All Screening evaluations must be completed and reviewed to confirm that potential patients meet all eligibility criteria. The Investigator will maintain a Screening log to record details of all patients screened and to confirm eligibility or record reasons for Screening failure, as applicable.
- Patient Reported Outcomes questionnaires should be completed by patients before study medication administration.
- The site should make every attempt to have the same Investigator complete the below assessments throughout the study for each patient.
- The maximum amount of blood collected from each patient over the duration of the study, not including any extra assessments that may be required, will be specified in the ICF. Repeat or unscheduled samples may be taken for safety reasons or for technical issues with the samples.

8.1 Efficacy Assessments

8.1.1 Lesion Counts—Abscess, Nodule and Draining Fistulas (tunnels)

The location and extent of HS will be assessed and recorded at the study visits outlined in the SoA ([Table 1](#)) by recording the affected anatomic location(s) of the disease, as well as the number of inflammatory and noninflammatory nodules, abscesses, and draining and nondraining fistulas in each of the locations ([Appendix 8](#)).

The information regarding location and extent of HS involvement will be used to determine the Hurley Stage and to calculate the HiSCR, the Hidradenitis Suppurativa-Physician's Global Assessment Scale (HS-PGA) and the International Hidradenitis Suppurativa Severity Score System (IHS-4).

The following areas will be evaluated at visits specified in the SoA to assess and record the extent of HS:

- left and right axillae
- left and right inframammary areas
- intermammary area

- left and right buttocks
- left and right inguino-crural folds
- perianal area and perineal area, and
- other (eg, abdominal fold, neck, back).

8.1.1.1 *Hidradenitis Suppurativa Lesions:*

- Inflammatory lesions: evidence of inflammation (eg, erythema, pain, warmth)
 - Nodule: should be raised, round lesion, can be a pyogenic granuloma-like lesion
 - Abscess: fluid (pus) filled
- Fistula/Tunnel/Sinus Tract: lesion draining to the skin, can be in direct connection with one another or localized closely to one another
 - Draining: if open at skin surface (ulcerated), will sometimes ooze a fluid
 - Nondraining: if not open to the skin surface, will not ooze
- Non-inflammatory lesion:
 - Non-inflammatory nodule: not inflamed or painful

8.1.1.2 *Hidradenitis Suppurativa Clinical Response*

Hidradenitis Suppurativa Clinical Response is defined as at least a 50% reduction from Baseline in the total AN count, with no increase in abscess and no increase in draining fistula counts relative to Baseline.

The HiSCR is defined by the status of 3 types of lesions (see definitions above):

- Abscesses
- Inflammatory nodules
- Draining fistulas

The definition for response to treatment based on HiSCR relative to Baseline (Day 1, Visit 2) is:

- At least 50% reduction in AN count
- No increase in number of abscesses
- No increase in number of draining fistulas

For this score, patients are defined as achievers or non-achievers. Patient achievers at any scheduled timepoint will have a HiSCR defined as at least a 50% reduction in abscess and inflammatory nodule count (AN count) and no increase in abscesses and no increase in draining fistulas relative to Baseline at that timepoint.

A patient is considered to be a HiSCR achiever only if all 3 criteria above are fulfilled ([Kimball et al, 2016b](#)).

The time required for Investigators to complete the HiSCR ranges from 1 to 2 minutes for patients with minimal disease, ie, 5 HS lesions in 2 anatomic locations, up to approximately 30 minutes for patients with multiple lesions in all 12 anatomic locations.

8.1.1.3 *International Hidradenitis Suppurativa Severity Score System*

The International Hidradenitis Suppurativa Severity (IHS-4) is a validated tool used to assess HS severity. The IHS-4 is calculated based on the clinical signs of HS: inflammatory nodules, abscesses and draining tunnels (fistulas and sinuses). The terms sinus tract and tunnel should be considered as synonyms of fistula ([Daxhelet 2020](#)).

The IHS-4 score (points) = (number of nodules multiplied by 1) + (number of abscesses multiplied by 2) + [number of draining tunnels (fistulas/sinuses) multiplied by 4].

A score of 3 or less signifies mild HS, a score of 4-10 signifies moderate HS and a score of 11 or higher signifies severe HS ([Zouboulis et al, 2017](#)).

8.1.2 Patient's Global Assessment of Skin Pain

The NRS30 – Patient's Global Assessment of Skin Pain will be completed daily by patients starting at the Baseline visit through Week 12 as outlined in the SoA ([Table 1](#)). On visit days, patients will complete the NRS30 – Patient's Global Assessment of Skin Pain at the study center prior to administration of the in-clinic morning dose of study treatment. Site personnel will witness the completion of the assessment.

The severity of the patient's skin pain will be assessed by completion of a numerical rating scale with 0 indicating no pain and 10 indicating the worst pain imaginable in a 24-hour recall period (maximal daily pain) ([Kimball et al, 2016](#)). Patients should be instructed to complete the assessment prior to the morning dose of study medication.

This questionnaire will be administered electronically and should take approximately 1 minute to complete.

8.1.3 Dermatology Life Quality Index

The Dermatology Life Quality Index (DLQI) is a 10-item validated questionnaire used to assess the impact of HS disease symptoms and treatment on QoL. It consists of 10 questions including a single “yes/no” question and 9 multiple choice questions with possible responses of “not at all,”

“a little,” “a lot,” or “very much.” These questions evaluate the impact of skin diseases on different aspects of a patient’s QoL over the prior week, including symptoms and feelings, daily activities, leisure, work or school, personal relationships, and the side effects of treatment.

Each question is scored using a 4-point scale which ranges from 0-3 based on a patient’s response: not at all/not relevant (0), a little (1), a lot (2) and very much (3) ([Basra 2015](#)).

Question 7, the single yes/no question is two-part question. The first part can be scored based on a response of “yes” (3) or “no/not relevant.” If “no/not relevant” is selected, part two of the question can be scored based on the following responses: not at all (0) little (1), a lot (2).

The total score of the DLQI (range of 0-30) is calculated by adding up the scores from each question. The higher the score, the greater the impact on a patient’s quality of life.

This questionnaire will be administered electronically and should take approximately 1 to 3 minutes to complete.

8.1.4 Hidradenitis Suppurativa-Physician’s Global Assessment

The HS-PGA scale is a 6-point scale used to assess ranges from clear to very severe ([Hidradenitis Suppurativa Trust, 2018](#)). It is used in clinical trials to measure clinical improvement in inflammatory nodules, abscesses and draining fistulas. The 6 stages are based on the presence and numbers of nodules, abscesses, and draining fistulas ([Kimball et al, 2012](#)). In the HS-PGA scale, Investigators will rate the counts of nodules (inflammatory and noninflammatory) abscesses and fistulas (both draining and nondraining) and assign a patient to 1 of 6 categories listed below.

Severity	Score	Definition
Clear	0	0 abscesses, 0 draining fistulas, 0 inflammatory nodules, and 0 non-inflammatory nodules
Minimal	1	0 abscesses, 0 draining fistulas, 0 inflammatory nodules, and presence of non-inflammatory nodules
Mild	2	0 abscesses, 0 draining fistulas, and 1 to 4 inflammatory nodules or 1 abscess or draining fistula (sum of abscesses and draining fistulas is 1) and 0 inflammatory nodules
Moderate	3	0 abscesses, 0 draining fistulas, and ≥ 5 inflammatory nodules or 1 abscess or draining fistula and ≥ 1 inflammatory nodule or 2 to 5 abscesses or draining fistulas (sum of abscesses and draining fistulas is 2 to 5) and < 10 inflammatory nodules
Severe	4	2 to 5 abscesses or draining fistulas and ≥ 10 inflammatory nodules

Very Severe	5	>5 abscesses or draining fistulas (sum of abscesses and draining fistulas >5)
-------------	---	-------------------------------------------------------------------------------

This questionnaire will be completed electronically by the Investigator and should take approximately 1-3 minutes to complete.

8.1.5 Hurley Staging System

The Hurley Staging System is used to assess and grade the progression of HS by placing patients in 1 of 3 groups or stages: mild (Hurley Stage I), moderate (Hurley Stage II), or severe (Hurley Stage III).

Hurley Stages defined:

- Stage I: Abscess formation, single or multiple, without sinus tracts and scarring
- Stage II: 1 or more widely separated recurrent abscesses with tract formation and scarring
- Stage III: Multiple interconnected tracts and abscesses across the entire area, with diffuse or near diffuse involvement

The Investigator will complete the Hurley Staging assessment for each affected anatomical area at each visit specified in the SoA ([Table 1](#)). If more than 1 stage is present in an area, the worst stage in each area should be applied.

8.1.6 Lesion Photography

Photographs of identified HS lesions will be taken at each study visit specified in the SoA ([Table 1](#)) for patients who consent to it. Sites will be required to submit the patient's Baseline photographs to Canfield Scientific's database. Canfield Scientific will supply all investigational sites with study-specific laptop and camera equipment to photograph each patient's identified target HS lesion treatment areas (at least 1 HS area but up to 2 unique target areas). Details regarding the use of the equipment and how to upload the photographs to the Canfield database will be supplied to the sites in the Photography Manual.

8.2 Safety Assessments

Planned time points for all safety assessments are provided in the SoA ([Table 1](#)).

8.2.1 Physical Examinations

- A complete PE will include, at a minimum, general appearance; skin; eyes; ears, nose, throat; head and neck; heart, chest, and lungs; abdomen; extremities; lymph nodes; musculoskeletal; neurological; and other body systems, if applicable, for describing the status of the patient's health.
- A targeted PE will include, at a minimum, signs of HS.

- Body weight and height (height at Screening only) will also be measured and recorded. Body mass index (BMI) will be calculated electronically in the eCRF. The patient should be dressed in lightweight clothing, without shoes.
- Investigators should pay attention to clinical signs related to previous illnesses. Any new abnormalities or worsening of existing abnormalities should be reported as AEs, as appropriate (see [Section 8.3](#)).
- See [Section 7.0](#) for discontinuation criteria based on skin toxicity.

8.2.2 Vital Signs

- Vital signs will be measured prior to dosing and immediately following dosing in a semi-supine position after \geq 5 minutes' rest without distractions (eg, television, cell phones). Vital signs (to be taken before blood collection for laboratory tests, when applicable) will consist of 1 body temperature measurement, 1 pulse rate measurement, 1 respiratory rate measurement, and 1 systolic and diastolic BP measurements. One repeat will be allowed for any abnormal BP readings.
- Abnormal, clinically significant vital sign results outside of the 1 allowable repeat will be recorded as AEs (see [Section 8.3](#)). If known, the underlying etiology for the abnormal clinically significant vital sign will be recorded as an AE rather than the vital sign itself.
- The BP and pulse measurements will be assessed with a completely automated device. Manual techniques will be used only if an automated device is not available.

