AE=adverse event; AN=abscess and inflammatory nodule count; BMI=body mass index; DLQI=Dermatology Life Quality Index; ECG=electrocardiogram; EOS=end of study; ET=early termination; HIV=human immunodeficiency virus; HS=hidradenitis suppurativa; hsCRP=high sensitivity C-reactive protein; HS-PGA=Physician Global Assessment Scale; mRNA=messenger RNA; NRS30= Numerical Rating Scale for Patient's Global Assessment of Skin Pain; PD=pharmacodynamic; PK=pharmacokinetic; SARS-CoV-2=severe acute respiratory syndrome coronavirus 2; TB=tuberculosis; WOCBP=women of childbearing potential.

[figure not shown]
- a. Triplicate 12-lead ECGs will be performed at least 30 seconds apart, in a supine position, after resting for at least 10 minutes (without external stimulation, e.g., talking, TV, noise) and submitted for central reading. Screening ECGs will be collected prior vital signs and blood samples. On Day 1 and 8, ECGs will be taken predose and 2 hours postdose. Patients not fasting on Day 1 and 8 will have an additional 4 hr postdose ECG. On Days 15, 29, 43, 57, and 85 ECGs will be performed as the last assessment in the clinic (as close to Cmax). See [Section 8.2.3](#) for additional details on collection parameters.
- b. Vital signs are to be taken before blood collection for laboratory tests. See [Section 8.2.2](#) for additional details on collection parameters.
- c. PK blood sampling times on Days 1, 8, and 85 will occur predose and 2 hours after the morning dose. Patients not fasting on Days 1 and 8 will have an additional PK sample collected at 4 hours postdose. If the patient objects to both blood draws at the 2hr and 4hr timepoint, the 4hr PK sample is more important to collect. Patients must remain in the clinic until 30 minutes after the morning postdose PK blood sampling is completed. See [Section 8.5](#) for additional details on collection parameters.
- d. PK blood sampling will occur prior to the morning dose on Days 15, 29, 43, and 57. See [Section 8.5](#) for additional details on collection parameters.
[REDACTED]
[REDACTED]
[REDACTED]
- g. The last dose of study treatment will be administered in the clinic on Day 85. The second dose of study treatment is not to be administered on Day 85.

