### **3.3.9. Presentations by Study Visit**

Scheduled and unscheduled assessments collected from Visit 1 through Visit 8 for all efficacy assessments and safety assessments (labs, vital signs, and ECG) will be assigned to an analysis visit window using the study day ranges described in [Table 1](#) and [Table 2](#). All study days up to and

---

including Day 1 are in the baseline-eligible analysis visit window. The last non-missing assessment in the baseline-eligible analysis visit window will be used in any summaries that present the baseline results with the exception of ECG interpretation where the best result from the triplicate values will be chosen. Day 1 post-dose ECG, PK and vital signs assessments will be analyzed as collected. Day 8 ECG assessments, Day 8 and 85 PK assessments, and Day 8, 15, 29, 43, 57 and 85 vital sign assessments will be windowed per Table 2, then each time point will be analyzed as collected. For all other assessments, for post-baseline analysis windows, if multiple assessments occur within a given analysis visit window, the result closest to the target study day, regardless of whether scheduled or unscheduled, will be used for summary presentations. If two measurements have the same distance to the target study day, the first assessment will be used in the summary presentations with the exception of ECG interpretation where the worst result from the triplicate values for the given visit and timepoint will be used. All assessments will be presented in the listings. In addition to the analysis visits indicated in Table 1 and Table 2, for patients who prematurely discontinue the study, data collected during the withdrawal visit will be used as an EOS assessment for these patients. The EOS assessment will be included in safety analyses.

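### Post-dose vital signs are read immediately after the tablet, so no scheduled blood-pressure reading falls near the 2-hour or Cmax time used for ECG and PK

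*Protocol*

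**What the plan says.** Protocol Section 8.2.2 sets two readings around the clinic dose: "Vital signs will be measured prior to dosing and immediately following dosing in a semi-supine position after" at least 5 minutes' rest. The vital-signs footnote to the Schedule of Assessments (footnote b) gives only an order, "Vital signs are to be taken before blood collection for laboratory tests", and refers back to Section 8.2.2. It names no post-dose clock time.

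The other post-dose assessments in the Schedule of Assessments are timed later:

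- **ECG, Days 1 and 8:** "On Day 1 and 8, ECGs will be taken predose and 2 hours postdose". Also, "Patients not fasting on Day 1 and 8 will have an additional 4 hr postdose ECG".
- **ECG, Days 15 to 85:** the last assessment in the clinic, placed as near to Cmax as possible.
- **PK, Days 1, 8 and 85:** "PK blood sampling times on Days 1, 8, and 85 will occur predose and 2 hours after the morning dose". Non-fasting patients on Days 1 and 8 have a further 4-hour sample.
- **PK, remaining visits:** "PK blood sampling will occur prior to the morning dose on Days 15, 29, 43, and 57".

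SAP Section 3.3.9 treats the second vital-sign set as a time point of its own: "Day 1 post-dose ECG, PK and vital signs assessments will be analyzed as collected". For Days 8 to 85 it windows vital signs by visit and then analyses each time point. Vital signs abnormalities are among the secondary endpoints in Protocol Section 3.0, and the analysis is descriptive (Protocol Section 9.4.2).

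**The concern.** An oral tablet needs time to be absorbed. A reading taken directly after swallowing it shows little of what that dose will do, particularly on Day 1, when no drug is on board beforehand. The ECG and PK times show when the sponsor expects exposure to be informative: 2 hours, with 4 hours added if the patient has eaten. The QT assessment is timed to that exposure and blood pressure is not.

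Two things are at stake. A short-lived rise or fall in blood pressure around peak could pass without a scheduled reading, and so might not be recorded as an adverse event under Section 8.2.2. In addition, a reader of SAP Table 14.3.5.1 may take a post-dose row as evidence about the effect of the dose just taken. SAP Section 3.3.9 encourages this by naming post-dose ECG, PK and vital signs together, although the vital signs come about 2 hours before the other two.

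**Working it through.** The plan states no figure for vital signs (no target effect, power or threshold), so there is none to reproduce. The check has two parts.

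**1. Times side by side (after the morning clinic dose)**

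| Visit | Blood pressure | ECG | PK |
|---|---|---|---|
| Days 1, 8 | immediate | 2 h (plus 4 h if not fasting) | 2 h (plus 4 h if not fasting) |
| Days 15, 29, 43, 57 | immediate | last assessment, aimed at Cmax | none post-dose |
| Day 85 | immediate | last assessment, aimed at Cmax | 2 h |

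No row has a blood-pressure reading at 2 hours or near Cmax. Footnote c keeps patients in clinic until 30 minutes after the post-dose PK draw, so they are present at 2 hours on Days 1, 8 and 85. Days 15 to 57 have no fixed post-dose time and no required stay.

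**2. Illustration of exposure at the immediate reading**

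Tmax and half-life are not in the visible text (Protocol Sections 2.3 and 4.3 are redacted). The following are assumptions: one compartment, first-order absorption, no lag, Tmax 1, 2 or 4 h, half-life 4 to 12 h, and a reading 5 to 10 minutes after the tablet.

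- Elimination rate: ke = ln 2 / half-life.
- Absorption rate: ka solves Tmax = ln(ka/ke)/(ka − ke).
- First dose: C(t) is proportional to exp(−ke·t) − exp(−ka·t).

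Example with Tmax 2 h and half-life 6 h: ke = 0.1155 and ka = 1.342 per hour.

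- C(5 min) = 0.9904 − 0.8942 = 0.096.
- C(10 min) = 0.9809 − 0.7996 = 0.181.
- C(2 h) = 0.7937 − 0.0683 = 0.725.
- Ratios to peak: 0.096/0.725 = 13% and 0.181/0.725 = 25%.

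Day 1 concentration as a share of peak, half-life 4 to 12 h:

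| Assumed Tmax | 5 min | 10 min |
|---|---|---|
| 1 h | 26–32% | 47–55% |
| 2 h | 12–15% | 23–29% |
| 4 h | 6–7% | 11–13% |

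Any absorption lag would lower these values.

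For steady state on twice-daily dosing, divide each exponential term by 1 − exp(−rate × 12 h). At Tmax 2 h:

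- The 5-minute level is 31% to 64% of the 2-hour level. Much of that is exposure already present before the dose. With a 6 h half-life, for example, trough is 33.5% of peak and the 10-minute level is 51.1%.
- The share of the trough-to-peak rise reached by 10 minutes in that example is (51.1 − 33.5)/(100 − 33.5) = 26%. Across half-lives of 4 to 12 h it is 24% to 31% at 10 minutes and 13% to 17% at 5 minutes.

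**The case against.** A reader might infer that the vital signs cannot detect a drug effect at all. The documents do not support that. Dosing is twice daily for 12 weeks. The SAP baseline is the last value before first dose (Section 3.3.8), and vital signs are summarised as change from baseline (Section 5.5.2). On Days 8 to 85 both readings are therefore on-drug values set against a drug-free baseline, and a sustained effect can show. In the Tmax 2 h illustration, the steady-state 5-minute level is 36% to 131% of the Day 1 2-hour level. The loss is clearest on Day 1.

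Nor do the documents support extending the point to pulse. The ECG machine calculates heart rate (Protocol Section 8.2.3), and the SAP summarises it with change from baseline (Section 5.5.3), at 2 hours or aimed at Cmax.

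It is also tempting to say that the immediate reading fails its purpose, or that the protocol contradicts itself. No visible passage says the reading is meant to capture a peak effect, and different clock times for different assessments are not in themselves a contradiction. The drug's acute blood-pressure profile may already be known from Phase 1; that cannot be judged here. The illustration also assumes that effect follows plasma concentration without delay, which no passage establishes.

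Other safeguards exist: adverse events are collected at every visit, clinically significant abnormal vital signs are recorded as adverse events, unscheduled visits are allowed, and a DSMB reviews unblinded safety data. None of these schedules a blood-pressure reading near peak, so the narrower gap stands.

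**Conclusion.** The point holds for blood pressure and for a transient, peak-related change, most clearly after the first dose. The timing gap follows from the documents alone. Its size does not. Under the stated assumptions the Day 1 reading sees about 6% to 55% of peak concentration, or 12% to 29% if Tmax is 2 hours. At the favourable end (Tmax 1 h, read at 10 minutes) about half of the peak is already present, so how closely the post-dose summary repeats the pre-dose one also depends on the unseen pharmacokinetics. The consequence is limited because the vital-sign analysis is descriptive. This is an inexpensive improvement to a named safety endpoint and not a flaw that undermines the safety assessment.

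**What to change.** Reconcile Section 8.2.2 with Schedule of Assessments footnotes a to c:

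- **Days 1 and 8:** take the existing post-dose vital-sign set at the 2-hour ECG/PK time point, before the blood draw. For non-fasting patients, state whether the 2-hour or the 4-hour time point is used.
- **Day 85:** take it at the 2-hour PK time point, before the blood draw.
- **Days 15 to 57:** pair it with the last-assessment ECG only if feasible, and record the actual time since dose, because these visits have no fixed post-dose time.
- **SAP:** label the time point in Table 14.3.5.1, so that a post-dose row shows when it was read.

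If the sponsor keeps the immediate reading, the protocol should state its purpose and the table should show its actual time.

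The cost is a changed sentence in Section 8.2.2, a Schedule of Assessments footnote and a table label. The number of measurements stays the same, and patients are already in clinic at 2 hours on Days 1, 8 and 85. Sites must re-sequence procedures around the ECG and the PK draw, which has a window of ±10 minutes (Section 8.5), and the immediate post-dose reading is given up.
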